Fuchs endothelial corneal dystrophy is currently treated by a variety of keratoplasty techniques, including full-thickness cornea transplantation (for Stages 3 and 4) and 2 techniques involving transplantation of a graft of donor endothelial cells on donor Descemet's membrane. Currently, most patients undergoing keratoplasty for FECD have Stage 2 disease and the procedure starts with descemetorhexis, removing an area of the roughened and irregular Descemet's membrane (including the central guttae) from the diseased cornea. The excised area is replaced with a graft of endothelial cells: either donor Descemet's membrane with a thin layer of corneal stroma (Descemet stripping endothelial keratoplasty [DSEK]), or, increasingly commonly, donor Descemet's membrane alone (Descemet's membrane endothelial keratoplasty [DMEK]).

Experience with failed grafts has indicated that even though there is an underlying abnormality of endothelial cells in FECD, areas of stroma exposed by descemetorhexis can be re-endothelialised and the migrated endothelial cells can maintain corneal transparency. Mathematical modelling of the healing of an inadvertent 5-mm diameter descemetorhexis in an elderly man without FECD suggested that normal healing is achieved by redistribution of peripheral endothelial cells into the central defect without any increase in the number of endothelial cells (Jullienne et al 2015). This led to the proposal that some cases of FECD, particularly those with relatively preserved peripheral endothelial cells, can be treated by descemetorhexis alone (Garcerant et al 2019).

There are limits to the ability of the endothelium to heal. In a recent analysis of cases of patients who underwent descemetorhexis without grafting as a possible treatment for FECD

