(compiled from multiple papers), 31 (65%) out of 47 cases eventually achieved a clear cornea, with healing taking place as early as 1 month after the procedure (Van den Bogerd et al 2018). If there was persistent oedema at 6 months, then it was unlikely to resolve. If corneal oedema did not clear, some patients' corneas cleared without residual stromal damage after DMEK performed as rescue therapy between 4 and 8.5 months after Descemet's membrane stripping (Van den Bogerd et al 2018). All keratoplasty procedures, including DMEK, are associated with risks of graft detachment, graft failure or immune rejection. There is a medical need for medication that can speed healing after descemetorhexis and that can help establish a high, functional ECD to maintain corneal transparency.

Ripasudil ophthalmic solution 0.4% (K-321) is a Rho-associated protein kinase (ROCK) inhibitor that has been marketed in Japan since December 2014 as Glanatec[®], with twice daily (BID) dosing for glaucoma and ocular hypertension. Studies in endothelial cells have indicated that K-321 can lead to reduction of apoptosis, enhancement of cell proliferation, and increased rates of migration, all of which may support endothelial healing (Kowa Company Ltd 2019). Moloney et al (2017) first reported use of a ROCK inhibitor to promote healing in patients with FECD treated with Descemet stripping only (DSO). More recently, Macsai et al (2019) reported results from a small study of 18 patients with FECD and central confluent guttae of up to 5 mm diameter who underwent DSO and were subsequently treated with either ripasudil ophthalmic solution 0.4% four times daily (QID) or no ripasudil for 2 months. Overall, patients who underwent DSO with ripasudil recovered vision more quickly [REDACTED]

[REDACTED] The patients in the no-ripasudil group had [REDACTED] while in the ripasudil group there was [REDACTED]. In the short-term studies (8 weeks duration and less) for the development of Glanatec, there were [REDACTED]

[REDACTED]
[REDACTED]
[REDACTED] (Kowa Company Ltd 2019).

Kowa proposes to pursue development of K-321 (ripasudil ophthalmic solution) for the following indication: “the treatment of Fuchs endothelial corneal dystrophy after descemetorhexis.” This will be the first Kowa-sponsored study in patients for this indication.

2 Study Objectives

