5.8.1 Descemetorhexis of the Study Eye

As a condition of participating in the study, each patient will undergo descemetorhexis of the investigator-selected study eye at Visit 2 (Day –1). See Section 6.1.2 for details.

In the absence of suitable local guidance or personal preference of the investigator, recommended post-descemetorhexis concomitant therapy consists [REDACTED] [REDACTED] instilled [REDACTED] and [REDACTED] instilled [REDACTED]. However, an investigator will be able to add [REDACTED] dosing after [REDACTED] if the investigator judges it necessary. When more than 1 different eye drop is administered (including study drug), the study drug must be administered first, followed by any non-study eye drop(s) after at least 5 minutes have passed (Section 5.2).

A patient must not be randomly assigned to study drug unless the excised diameter satisfies inclusion criterion 5 (Section 4.1.1).

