6.1.2 Descemetorhexis of the Study Eye

Each patient will undergo descemetorhexis of the investigator-selected study eye at Visit 2 (Day -1). A digital photo of the study eye must be taken immediately before and immediately after descemetorhexis at Visit 2. The investigator will perform descemetorhexis to remove central confluent guttae, removing an area of Descemet membrane with a diameter of [REDACTED]. The longest diameter and the shortest diameter must be recorded in the eCRF. The procedure must be recorded by video to record potential differences in technique among investigators. Also, immediately after the operation, the stripped area will be recorded by photo or video with an adjacent scale to measure the area removed. Detailed guidance for performing the study eye descemetorhexis will be provided in the study manual.

Recommended post-descemetorhexis concomitant therapy is described in Section 5.8.1.

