6.7 Sample Collections

Sample collection, processing, and shipping must be performed according to local laboratory requirements and consistent with detailed procedures described in the study manual.

The volume of blood sampled is planned to be less than 20 mL in a single day and less than 35 mL over the entire study.

7 Statistical and Analytical Plan

A study eye will be identified for each patient. Unless otherwise specified, efficacy will be summarised for the study eye only. Ocular safety summaries by eye will be presented separately for the study eye and the non-study eye. Baseline measurements are the last measurements taken during the screening period (before Visit 2).

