7.7.1 Analysis of Primary Efficacy Endpoint

The primary analysis of central corneal ECD will be performed on the study eye within the FAS via a Wilcoxon rank sum test and will be based on assessments performed by specular microscopy. Testing will be performed in a pairwise manner with each dosing regimen (QID and BID) of K-321 0.4% compared to placebo. For each dosing regimen, the following 2-sided hypothesis will be tested

$H_0: \Delta = 0$ versus $H_a: \Delta \neq 0$

where Δ is the shift in location in central corneal ECDs between the active and placebo groups being compared: ie,

$X_i = e_i$ for $i = 1$ to n for the placebo patients

$Y_j = e_j + \Delta$ for $j = 1$ to m for the K-321 patients

The Hodges-Lehmann estimate (Hodges and Lehmann 1963) for the shift in location (eg, the median of all differences $d=Y_j - X_i$) and Moses 95% CI (Moses 1965) will also be presented.

Week 12 assessments that are unable to be performed due to corneal oedema will be [REDACTED]
[REDACTED]
[REDACTED].

Week 12 assessments that are [REDACTED] due to patient withdrawal or missed visit will be [REDACTED]. Patients who receive a rescue keratoplasty performed prior to Week 12 will be [REDACTED]
[REDACTED]
[REDACTED]
[REDACTED]
[REDACTED]

Sensitivity analyses will be performed by repeating the above analysis and [REDACTED] [REDACTED] for the PPS. The primary analysis methods will also be repeated for the FAS using [REDACTED]
[REDACTED] Additionally, analyses will be performed using assessments performed by HRT for the subset of patients for which the assessments are available.

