7.7.5 Other Analyses

7.7.5.1 Patient Demographics and Other Baseline Characteristics

Descriptive statistics will be provided by treatment group for patient demographics and all ocular and baseline characteristics. Relevant medical history (ocular and non-ocular) and current medical conditions will be tabulated by treatment group. Ocular summaries will be presented for the study eye and the non-study eye. Other relevant baseline information will be listed and summarised as appropriate with descriptive statistics. Analyses will be based on the FAS.

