| Difference to Placebo [1]         |                      |                      |                    |
| p-value by Wilcoxon Rank Sum Test | X.XXXX               | X.XXXX               |                    |
| Hodges-Lehmann Estimate           | X.X                  | X.X                  |                    |
| Moses 95% Confidence Interval     | (XX.X, XX.X)         | (XX.X, XX.X)         |                    |
| Central Corneal ECD at Week 1     |                      |                      |                    |
| n                                 | XX                   | XX                   | XX                 |
| Mean (SD)                         | XX.X (XX.XX)         | XX.X (XX.XX)         | XX.X (XX.XX)       |
| Median                            | XX.X                 | XX.X                 | XX.X               |
| Q1, Q3                            | XX.X, XX.X           | XX.X, XX.X           | XX.X, XX.X         |
| Min, Max                          | XX, XX               | XX, XX               | XX, XX             |
| Difference to Placebo [1]         |                      |                      |                    |
| p-value by Wilcoxon Rank Sum Test | X.XXXX               | X.XXXX               |                    |
| Hodges-Lehmann Estimate           | X.X                  | X.X                  |                    |
| Moses 95% Confidence Interval     | (XX.X, XX.X)         | (XX.X, XX.X)         |                    |

...  
 Note: LOCF = last-observation-carried, ECD = Endothelial Cell Density  
 Baseline is defined as the last measurement including unscheduled assessments prior to the administration of first dose of [REDACTED] treatment.  
 Central corneal ECD (both baseline and post-baseline) that are unable to be performed due to corneal oedema are [REDACTED]. Assessment images that are unable to be analysed and categorized as [REDACTED].

[REDACTED] and [REDACTED] by [REDACTED] are [REDACTED]  
[REDACTED]  
[REDACTED]  
[REDACTED]  
[REDACTED] is based on the Wilcoxon rank sum test. The [REDACTED] between [REDACTED] treatment groups and the Moses CIs were estimated with the Hodge-Lehmann method.  
Source Data: Listing 16.2.6.1

<DIRECTORY PATH>PROGRAM NAME Executed: DDMMYYYY hh:mm

Prog Notes: 1. Repeat for scheduled visits.

Table 14.2.1.44

Change from Baseline in Central Corneal Thickness ( $\mu\text{m}$ ) of Study Eye by Visit (LOCF) via Wilcoxon Rank Sum Test  
(Full Analysis Set)

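### Should the primary ECD comparison be backed by an analysis adjusted for stripped diameter, with diameter tabulated by arm?

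*Protocol*

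**What the plan says.** Section 7.7.1 sets the primary comparison: "The primary analysis of central corneal ECD will be performed on the study eye within the FAS via a Wilcoxon rank sum test". Each K-321 regimen is compared with placebo, with a Hodges-Lehmann estimate and Moses interval alongside. Section 7.4 plans 20 patients per arm. Section 5.1 describes blocked randomisation and names no stratification factor. Section 7.6 rules out subgroup analyses because the trial is small.

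Stripped size is known before allocation. Section 5.8.1 says: "A patient must not be randomly assigned to study drug unless the excised diameter satisfies inclusion criterion 5". Section 6.1.2 says: "The longest diameter and the shortest diameter must be recorded in the eCRF". It also asks for a scaled image of the stripped bed so that the removed area can be measured.

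On tabulation, Section 7.7.5.1 says: "Descriptive statistics will be provided by treatment group for patient demographics and all ocular and baseline characteristics". A later sentence there extends the summaries to other relevant baseline information where suitable. The opening of Section 7 takes baseline as the last screening-period value, before Visit 2. The note to Table 14.2.1.43 in the SAP addendum reads: "Baseline is defined as the last measurement including unscheduled assessments prior to the administration of first dose".

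The only SAP supplied is an addendum written after the Week 12 unmasking. It says that it does not repeat the analyses in primary SAP v2.0.

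**The concern.** The Introduction to the protocol cites modelling in which "normal healing is achieved by redistribution of peripheral endothelial cells into the central defect". On that account a larger defect spreads the same cells more thinly, so stripped area would be expected to predict central ECD at Week 12. The variable is measured before treatment, costs nothing extra to collect, and may vary across about 30 sites with about 2 patients each.

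With 20 per arm, chance can leave one arm with larger defects. If area matters, the unadjusted p-value in such a trial partly reflects the imbalance, and without by-arm diameters a reader could not see it. The two baseline definitions seem to make this worse. Diameter is measured at Visit 2, so the Section 7 definition would leave it out, while the addendum's definition would let it in. At stake is the interpretation of the primary result in an unlucky trial. The natural remedy would be a by-arm table and a supportive rank analysis of covariance (Quade's method) on stripped area.

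**Working it through.** **The plan's own figure.** 3 arms x 20 = 60, which agrees with the stated total of about 60. The planned difference, SDs and power are blacked out, so the power calculation cannot be reproduced.

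**Inputs.** From the documents: 20 per arm, two-sided 0.05, Wilcoxon test, and about 10% of Week 12 values unmeasurable and scored zero (Section 7.4). Assumed, because the documents give no figure: area explains a share R² of the variance in measurable ECD, with R² from 0 to 0.30; zeros are unrelated to area; the drug effect is set to give about 81% Wilcoxon power. Rescue handling before Week 12 is blacked out and not modelled.

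**Step 1: how often is area imbalanced?** In SD units, the difference between two arm means has standard error sqrt(2/20) = 0.316.

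P(difference of at least 0.5 SD) = 2 x [1 - Phi(0.5/0.316)] = 2 x [1 - Phi(1.58)] = 0.114.

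For at least one of the two comparisons that share the placebo arm, simulation gives 0.20. These figures hold for any roughly normal covariate at this sample size; nothing in them is particular to stripped area.

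**Step 2: what does imbalance do to the false-positive rate?** Simulated under no drug effect, 200,000 two-arm trials per R²:

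| R² | Wilcoxon, imbalance at least 0.5 SD | Wilcoxon, otherwise | Quade, imbalance at least 0.5 SD |
|---|---|---|---|
| 0.04 | 5.8% | 4.7% | 4.2% |
| 0.10 | 7.2% | 4.6% | 4.3% |
| 0.20 | 9.1% | 4.3% | 4.1% |
| 0.30 | 11.4% | 4.1% | 4.4% |

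Recombining the Wilcoxon columns gives the overall rate:

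- R² 0.10: 0.114 x 7.2 + 0.886 x 4.6 = 0.82 + 4.08 = 4.9%
- R² 0.30: 0.114 x 11.4 + 0.886 x 4.1 = 1.30 + 3.63 = 4.9%

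The excess in unlucky trials is offset by conservatism in the rest.

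**Step 3: how many false wins for drug are at issue?** With no drug effect, half of the false positives favour drug. The excess of Wilcoxon over Quade within imbalanced comparisons, per 100 comparisons of any kind, is:

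- R² 0.04: 0.114 x (5.8 - 4.2) / 2 = 0.09
- R² 0.10: 0.114 x (7.2 - 4.3) / 2 = 0.17
- R² 0.20: 0.114 x (9.1 - 4.1) / 2 = 0.29
- R² 0.30: 0.114 x (11.4 - 4.4) / 2 = 0.40

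**Step 4: how much power would adjustment bring if it were primary?** Quade minus Wilcoxon, at about 81% Wilcoxon power, is -0.6, +0.2, +1.2, +2.8 and +4.5 points at R² 0, 0.04, 0.10, 0.20 and 0.30. If zeros also depend on area (a further assumption, latent correlation 0.5), the gains are +0.6, +3.0, +5.0, +7.5 and +9.8 points. A supportive analysis delivers none of this, because the Wilcoxon remains the test on which the trial is judged.

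**Step 5: is the table missing?** Stripped diameter is an ocular characteristic recorded before treatment. Section 7.7.5.1 covers ocular characteristics in general, adds other relevant baseline information, and names no individual variable, so silence on diameter is not exclusion. The two baseline definitions speak of a last measurement. That is wording for repeated measures that feed change scores, and it hardly bears on a surgical dimension recorded once. An analyst preparing baseline tables for a descemetorhexis trial would include the stripped dimensions under this text.

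**The case for a change.** The best case for acting is that it is nearly free. Roughly one trial in five would have a notable area imbalance in at least one primary comparison. The data are already collected, the covariate precedes randomisation, and rank adjustment copes with zero-scored eyes. A single covariate fixed in writing limits analyst choice, and labelling the analysis supportive leaves the type I error of the primary test alone.

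Much of this stands as general good practice. Seeing the stripped dimensions by arm does help a reader. It does not show a defect here, for four reasons.

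- **Prognostic value is unsupported.** The redistribution account comes from one eye without FECD. The protocol also credits the drug with "enhancement of cell proliferation, and increased rates of migration", and entry criteria restrict the diameter. Baseline ECD, peripheral cell status or surgical technique could equally be proposed, and nothing in the documents ranks area above them.
- **Timing.** The addendum follows the Week 12 unmasking. Unless SAP v2.0 already has the analysis, choosing a covariate now is a post hoc choice.
- **Absence is unproven.** Parts of the sensitivity text in Section 7.7.1 are blacked out, Section 7.7 leaves details to the SAP, and SAP v2.0 is not supplied.
- **Output.** Quade's method gives a p-value with no estimate in cells/mm², so it could disagree with the Hodges-Lehmann and Moses results without explaining why.

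**Conclusion.** No change to the plan is needed. The unadjusted Wilcoxon test holds its level at 4.8% to 5.0% across R² from 0 to 0.30. Within the roughly 11% of comparisons with an area imbalance of 0.5 SD or more, leaving area out adds about 0.1 to 0.4 false wins for drug per 100 comparisons overall, and only if area explains 4% to 30% of the variance. If it explains none, adjustment would cost about half a point of power.

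Omitting a covariate of unproven value in a phase 2 trial of 60 patients is a fair trade-off. The by-arm table is a detail that Section 7.7.5.1 already allows and analysts would fill sensibly; the scaled image required by Section 6.1.2 provides for measuring the removed area. Anyone holding SAP v2.0 can confirm whether the stripped dimensions are listed there. An area-adjusted rank analysis run after unmasking would be optional, post hoc and for interpretation only.

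The figures rest on the assumed range of R², a roughly normal covariate and 10% zeros. The validity of the primary test rests on randomisation and not on R².

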7.7.3 Analyses of Exploratory Efficacy Endpoints

Exploratory endpoints will be summarised for the FAS. Assessments after rescue keratoplasty will be [REDACTED]. Endpoints will be analysed in a similar manner to the secondary efficacy endpoints.

Endpoints based on continuous measures will be analysed by pairwise Wilcoxon rank sum tests comparing each active K-321 0.4% treatment regimen to placebo with the Hodges-Lehmann estimate for the difference in medians and Moses 95% CI for the difference in medians also presented.

Endpoints based on the number and percentage of patients achieving the endpoint will be analysed by pairwise Pearson chi-square tests comparing each active K-321 0.4% treatment regimen to placebo with the 95% CI for the difference in percentage of patients achieving the endpoint also presented.

Endpoints based on time-to-event endpoints will be analysed by pairwise log-rank tests comparing each active K-321 0.4% treatment regimen to placebo with Kaplan-Meier estimates and plots also presented. Patients who complete follow-up or discontinue the study without achieving the specified endpoint will be [REDACTED]

[REDACTED] Patients who receive rescue keratoplasty will be [REDACTED]
[REDACTED]

7.7.4 Safety Analyses

Safety parameters include monitoring of AEs, TEAEs, vital sign measurements, laboratory examinations, slit-lamp biomicroscopy, IOP, and ophthalmoscopy.

Safety data will be summarised and listed with no statistical hypothesis testing performed. Continuous variables will be summarised using the mean, the SD, median, minimum value, and maximum value. Categorical variables will be summarised using frequency counts and percentages.

7.7.4.1 Adverse Events

All AEs will be listed and all TEAEs will be summarised. Adverse events will be deemed treatment-emergent if the onset date is on or after the date of first treatment. Events which are not treatment-emergent will be listed separately and together with all other AEs. AEs will be summarised separately for the treatment period, the tapering phase, and the 9-month follow-up period. Ocular TEAEs will be summarised separately from non-ocular TEAEs. Ocular TEAEs will be summarised separately for the study eye and non-study eye.

Treatment-emergent AEs will be summarised by treatment group, presenting the number and percentage of patients having a TEAE in each system organ class and having each individual TEAE based on the preferred term. Treatment-emergent AEs will also be tabulated according to intensity and causality. Patients who experienced multiple TEAEs for a preferred term will be counted once, similarly for patients with multiple TEAEs per system organ class.

Deaths, SAEs, and TEAEs leading to discontinuation of study treatment will be listed separately and, if appropriate, summarised by treatment group, system organ class and preferred term.

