5.8.2 Rescue Surgical Procedures

Penetrating keratoplasty or endothelial keratoplasty may be offered as rescue surgical procedures to an enrolled patient if the investigator judges that endothelial healing is not complete at Week 12 (Visit 9), or earlier if the investigator considers that the patient needs urgent treatment. If the rescue surgery is performed, the dosing with study drug must be

discontinued immediately (without tapering) and the patient will attend all planned study visits including the follow-up period.

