6.3.2.2 Eliciting and Documenting Adverse Events

The investigator is responsible for reporting AEs that are observed or reported during the study, regardless of their relationship to study drug or their clinical significance. Serious AEs will be collected from the time that the patient gives consent to participate in the study until 30 days after the date of last dosing or of completion or withdrawal from the study, whichever is latest. All AEs will be collected starting from the time that the patient gives consent until the date of completion or withdrawal from the study.

Serious AEs that occur more than 30 days after the last dose of study drug or after exit from the study, whichever is later, need not be reported unless the investigator considers them related to study drug.

At each study visit, patients will be asked a standard non-leading question to elicit any medically related changes in their well-being. They will also be asked if they have been hospitalised, had any accidents, had any eye surgery, used any new medications, or changed concomitant medication regimens (both prescription and over-the-counter medications).

In addition to patient observations, AEs identified from any study data (eg, laboratory values, physical examination findings) or identified from review of other documents that are relevant to patient safety will be documented on the AE page in the eCRF.

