7.7.4.4 Intra-Ocular Pressure

All IOP data will be listed. Observed values at each visit and change from baseline values for IOP evaluations will be summarised descriptively by treatment group for the study eye and non-study eye.

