7.7.4.5 Slit-Lamp Biomicroscopy and Ophthalmoscopy

Ocular findings will be evaluated by the following criteria:

- Normal
- Abnormal (NCS)
- Abnormal with clinical significance (CS)

Data from all slit-lamp biomicroscopy and ophthalmoscopy assessments will be listed. The number and percentage of patients with at least 1 treatment-emergent CS abnormality by ocular assessment will be summarised for each treatment group for the study eye and non-study eye. An abnormality will be deemed treatment-emergent if the onset date is on or

after the date of first treatment. A patient will be counted once even if the patient experiences more than 1 treatment-emergent CS abnormality.

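### The protocol's safety sections and the SAP addendum do not separate study-eye data at rescue keratoplasty, so IOP at Weeks 16 to 52 and slit-lamp and ophthalmoscopy counts mix graft and drug effects

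*Protocol*

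**What the plan says.** Protocol 5.8.2 allows keratoplasty when healing is judged incomplete at Week 12, "or earlier if the investigator considers that the patient needs urgent treatment". Study drug is then "discontinued immediately (without tapering) and the patient will attend all planned study visits including the follow-up period". Under 6.3.2.2, "All AEs will be collected starting from the time that the patient gives consent until the date of completion or withdrawal from the study".

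The safety sections, which carry no redaction, then set these rules:

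- **Adverse events (7.7.4.1).** An event is treatment-emergent if it starts on or after first treatment, with no end point. "AEs will be summarised separately for the treatment period, the tapering phase, and the 9-month follow-up period". Treatment-emergent events are also shown by system organ class, preferred term, intensity and causality.
- **IOP (7.7.4.4).** "Observed values at each visit and change from baseline values for IOP evaluations will be summarised descriptively by treatment group", for each eye.
- **Slit-lamp and ophthalmoscopy (7.7.4.5).** "The number and percentage of patients with at least 1 treatment-emergent CS abnormality by ocular assessment will be summarised for each treatment group". The onset rule is the same open-ended one, and a patient counts once.

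None of these mentions rescue keratoplasty. The efficacy sections (7.7.1 to 7.7.3) each contain a statement on how rescue is handled, with its content blacked out. The SAP addendum also states rescue handling for its added efficacy analyses and adds a time-to-rescue analysis. It adds no safety analysis.

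**The concern.** Safety and tolerability of K-321 out to 52 weeks is a secondary objective (Protocol 2.2). Rescue is a second operation on the study eye, and the Introduction warns that "All keratoplasty procedures, including DMEK, are associated with risks of graft detachment, graft failure or immune rejection". It is offered when healing is judged incomplete, and healing is what K-321 is meant to improve. The proportion rescued may therefore differ between groups because of treatment.

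If placebo has more rescues, graft-related findings raise the placebo figures and can hide a true ocular signal on K-321. If a K-321 group has more rescues, the same findings can look like drug harm. Patients are not to use study drug after about Week 14, so from Week 16 the tables should show after-effects of the drug. Findings from grafted eyes are added to them without a marker.

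**Working it through.** There is no plan figure to reproduce: the documents state no rescue rate, no complication rate and no safety power. The check is of what separates graft effects from drug effects in each safety table, followed by an illustration of scale.

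**1. What separates the two in each table**

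- Adverse events: a calendar split into three periods, plus causality and preferred term. Rescue before Week 12 falls in the treatment period. Later rescue mostly falls in follow-up. A rescued patient takes no tapering drug, and his or her place in the tapering-phase table is not stated.
- IOP: by visit only. Visits up to Week 12 are affected only by urgent early rescue. Weeks 16, 20, 24, 38 and 52 are exposed.
- CS slit-lamp and ophthalmoscopy abnormalities: one ever/never count from first treatment to study end, with no period split and no causality table.

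**2. IOP, on assumed inputs**

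Spurious difference in group means = (difference in proportion rescued) × (mean IOP change per rescued eye). The documents do not say how keratoplasty changes IOP, so both inputs are assumptions: 3 to 8 mm Hg per rescued eye, and 10 to 34 percentage points difference in rescue.

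- Low: 0.10 × 3 = 0.3 mm Hg
- Middle: 0.24 × 5 = 1.2 mm Hg
- High: 0.34 × 8 = 2.7 mm Hg

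The 34% anchor comes from the Introduction: 31 of 47 eyes cleared without a graft, so 16/47 = 34% did not. Those eyes failed to clear; they were not all rescued, so 34% is an upper anchor for placebo. For comparison, 7.4 assumes about 10% unmeasurable ECD at Week 12 because of oedema.

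**3. Ever/never CS abnormality, on assumed inputs**

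A rescued eye changes this count only if it had no counted abnormality before rescue. Let r be the proportion rescued, g the chance of a graft-related CS finding, and h the share of rescued eyes not already counted. Then

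spurious difference (placebo minus K-321) = (r placebo − r K-321) × g × h.

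- h = 0 (every rescued eye already counted): 0 points, whatever r and g are.
- h = 0.9 (10% background, independent of rescue), rescue 20% v 10%, g = 25%: 0.10 × 0.25 × 0.9 = 2.25 points, less than half a patient in 20.
- h = 0.9, rescue 34% v 10%, g = 50%: 0.24 × 0.50 × 0.9 = 10.8 points.
- h = 0.9, rescue 34% v 10%, g = 75%: 0.24 × 0.75 × 0.9 = 16.2 points.

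An eye that needs a graft is likely to have had an abnormal cornea first, so h may be well below 0.9 and these non-zero values lean high. With equal rescue the difference is nil; with more rescue on K-321 the sign reverses.

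**4. Chance imbalance**

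If each of two groups of 20 has a true rescue rate of 20% (assumed), the numbers rescued differ by 3 or more with probability 0.32. Imbalance does not require a drug effect.

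**The case against.** Several points on the other side are sound, and they limit the finding.

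- **The primary SAP.** A reader might infer that the trial's safety analysis has no rescue cut at all. That cannot be shown. Protocol 7.7 leaves details to the SAP, and the addendum says that it does not repeat what SAP v2.0 defines. Only the protocol and the addendum can be said to lack the cut.
- **Grouping.** A reader might infer that graft events are charged to the randomised drop. The safety set in 7.5 groups by treatment actually received.
- **Size for adverse events.** A reader might infer that each rescued patient adds one whole patient in 20 to the overall treatment-emergent rate. Section 6.3.2.1 requires the condition that leads to a procedure to be reported as an AE, so many rescued patients should already be counted. Any shift would show mainly by preferred term and in the follow-up table.
- **Existing safeguards.** Graft detachment, failure and rejection identify themselves by preferred term. Causality is tabulated, although it is the investigator's judgement and the definition of unrelated in 6.3.2.3 does not name surgery. All AE, IOP and ocular data are listed, so individual cases can be traced among about 60 patients.
- **The remedy has its own bias.** Cutting at rescue conditions on an outcome that arises after randomisation. It removes the worst-healing eyes from later visits, perhaps unequally.

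All-data safety summaries are also a legitimate descriptive choice, and no safety test is planned. These points support keeping the all-data tables. They do not supply the missing separation for IOP or for CS findings, where neither a causality table nor a preferred term helps.

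**Conclusion.** The point holds in a limited form. The protocol and the SAP addendum specify no separation of study-eye safety data at rescue keratoplasty, although rescued patients stop drug and "the patient will attend all planned study visits including the follow-up period". The gap is clearest for study-eye IOP at Weeks 16 to 52 and for the ever/never CS counts. It is smaller for treatment-emergent AEs.

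The size and direction of any distortion are unknown. The ranges above show only that it can run from nothing to an amount that matters with 20 per group; they are not estimates for this trial. The conclusion assumes that SAP v2.0 does not already contain the separation. It does not touch the primary endpoint, but it does affect how a stated secondary objective can be read.

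**What to change.** First check SAP v2.0. If it has no such rule, make these additions for 7.7.4.1, 7.7.4.4 and 7.7.4.5:

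1. Keep the all-data tables as the main record.
2. Add supplementary summaries by group of study-eye ocular treatment-emergent AEs, CS slit-lamp and ophthalmoscopy abnormalities, and IOP, using only data before the date of rescue keratoplasty.
3. List or tabulate study-eye events and findings on or after that date separately, with the number rescued in each group as denominator.
4. Show the number rescued per group beside these tables. Take it from the surgery records: the addendum's time-to-rescue table (14.2.1.42) also counts certain withdrawals as rescue and uses the full-analysis set.
5. State in the SAP that the pre-rescue summaries lose the worst-healing eyes at later visits, possibly unequally by group, and must be read beside the all-data tables.
6. If the additions are made now, label them as defined after the Week 12 unmasking, as the addendum does for its other analyses.

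The cost is one date flag and a few extra tables. Section 5.8 already requires surgical procedures to be recorded in the eCRF, and the time-to-rescue analysis already needs the date, so no new data are collected.
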